1.3.3 Hepatocellular Carcinoma and PSMA

It has been shown that PSMA can be expressed not only on prostate cancer cells, but also on cell lines of other malignancies, as well as tumor endothelium. A recent publication reported that nearly 95% of hepatocellular cancers stained positive for PSMA in the tumor vasculature. Zhu et al. [22] suggested that the process of endothelial cell recruitment to HCC occurs early and throughout the process of hepatic tumorigenesis, making an endothelial cell tracer an ideal marker to detect early disease. In a recent study assessing 100 HCC tissue samples using immunohistochemical staining, Jiao and collaborators [23] reported PSMA expression in more than 50% of tumor-associated vasculature in 26% of tissues, and PSMA expression in less than 50% of vasculature in 48% of tissues. Furthermore, high vascular PSMA expression was also associated with poor prognosis in participants with HCC, and could be used as an independent prognostic marker for HCC [23]. Tolkach et al. [24] found that the majority of hepatocellular carcinomas (89.9%) show high levels of PSMA expression on tumor neovasculature and on canalicular membrane of the tumor cells (4.1% of tumors) [24]. To date, most of the reported findings with PSMA-targeted PET radiotracers in HCC have been in few case reports [25] and small case series [26]. Recently, ⁶⁸Ga-PSMA PET imaging showed encouraging preliminary results for imaging HCC in a small cohort of 7 participants. ⁶⁸Ga-PSMA PET-CT showed superiority over ¹⁸F-FDG PET-CT in imaging participants with HCC. All but a single tumor lesion were associated with ⁶⁸Ga-PSMA uptake higher than that of the surrounding liver

parenchyma (**Figure 2** and **Figure 3**), with a mean uptake 3.6 times higher than that of the background liver. The increased ⁶⁸Ga-PSMA uptake in HCC was corroborated by the results of immunohistochemistry analysis showing PSMA staining of the endothelial cells lining of vessels that are penetrated by tumor. Furthermore, ⁶⁸Ga-PSMA PET appeared to differentiate necrotic from viable tumor (**Figure 3**), which could dramatically improve detection of HCC recurrence following local ablative therapies [26]. In another recent study, Kuyumcu et al. [27] was able to visualize advanced HCC using ⁶⁸Ga-PSMA-PET/CT in 16 out of 19 cases with high tumor-to-background ratio. Interestingly, ⁶⁸Ga-PSMA standard uptake value (SUV_{max}) correlated with participant overall survival [27].

Few direct comparisons between ¹⁸F-DCFPyL and ⁶⁸Ga-PSMA-PET have been reported in prostate cancer population and only in one manuscript. Dietlein et al. [28] reported comparable biodistributions for both tracers, but slightly higher sensitivity for ¹⁸F-DCFPyL compared to ⁶⁸Ga-PSMA-11 (88% vs 66%) in participants with biochemical recurrence of prostate cancer.

[figure not shown]

Figure 2. Enhancing HCC. Increased uptake of ⁶⁸Ga-PSMA was seen within the tumor at the left liver lobe (arrows) as well as in tumor thrombus in the left portal vein (arrowheads). These lesions showed no significant FDG avidity.

[figure not shown]

Figure 3. HCC lesions with mosaic contrast enhancement on CT angiography. Increased ⁶⁸Ga-PSMA uptake was identified only in the enhancing area (arrows). Lesions were non-FDG-avid.

1.3.4 ¹⁸F-DCFPyL in HCC

We propose to expand clinical work using ¹⁸F-DCFPyL PET imaging in prostate cancer participants, and evaluate its usefulness in detecting sites of hepatocellular carcinoma. ¹⁸F-DCFPyL distribution and tumor uptake will be compared with the results of CT, and /or MRI.

This may provide data to support a future trial using ¹⁸F-DCFPyL PET/CT, define its role in the diagnosis and surveillance of HCC, especially following treatment. This study should offer insights into how and when ¹⁸F-DCFPyL could be used in the clinical setting to direct proper management.

2 ELIGIBILITY ASSESSMENT AND ENROLLMENT

2.1 ELIGIBILITY CRITERIA

2.1.1 Inclusion Criteria

- 2.1.1.1 High radiological suspicion of hepatocellular carcinoma (LR4 or LR5 based on the most current version of LI-RADS) with at least one measurable lesion on standard imaging modality (CT and/or MRI).
- 2.1.1.2 Eligible for local therapies (included but not limited to surgical resection, stereotactic radiation therapy, transarterial chem/radio/bland embolization, microwave ablation, radiofrequency ablation).
- 2.1.1.3 Ability to take oral medication and be willing to adhere to the study intervention regimen.
- 2.1.1.4 Age \geq 18 years.
- 2.1.1.5 ECOG performance status \leq 2 (see [Appendix A](#)).
- 2.1.1.6 Known human immunodeficiency virus (HIV)-infected individuals must be on effective anti-retroviral therapy with undetectable viral load within 6 months.
- 2.1.1.7 Known chronic hepatitis B virus (HBV) infected individuals, must be on suppressive therapy with undetectable viral load.
- 2.1.1.8 Individuals with a history of hepatitis C virus (HCV) infection must have been treated and cured.
- 2.1.1.9 The effects of ¹⁸F-DCFPyL (study drug) on the developing human fetus are unknown. For this reason and because this agent as well as other therapeutic agents used in this trial are known to be teratogenic, women of child-bearing potential and men must agree to use adequate contraception (hormonal or barrier method of birth control; abstinence) prior to study entry and for 2 months after each study PET/CT imaging. Should a woman become pregnant or suspect she is pregnant while she or her partner is participating in this study, she should inform her treating physician immediately.
- 2.1.1.10 Ability of subject to understand and the willingness to sign a written informed consent document.

2.1.2 Exclusion Criteria

- 2.1.2.1 History of allergic reactions attributed to compounds of similar chemical or biologic composition to ¹⁸F-DCFPyL or other agents used in study.
- 2.1.2.2 Uncontrolled intercurrent illness including, but not limited to, ongoing or active infection, symptomatic congestive heart failure, unstable angina pectoris, cardiac arrhythmia, or psychiatric illness/social situations that would limit compliance with study requirements.
- 2.1.2.3 Subjects with severe claustrophobia unresponsive to oral anxiolytics.
- 2.1.2.4 Other medical conditions deemed by the principal investigator (or associates) to make the subject unsafe/ineligible for protocol procedures.
- 2.1.2.5 Subjects weighing > 350 lbs (weight limit for scanner table), or unable to fit within the imaging gantry.
- 2.1.2.6 Serum creatinine > 2 times the upper limit of normal.
- 2.1.2.7 Pregnant women are excluded from this study because ¹⁸F-DCFPyL is an agent with the potential for teratogenic or abortifacient effects. as well as other agents used in this trial are known to be teratogenic.

2.2 RECRUITMENT STRATEGIES

This protocol may be abstracted into a plain language announcement posted on NIH websites and on NIH social media platforms. Participants will also be identified via internal referrals from each participating site institution, and outside referrals.

2.3 SCREENING EVALUATION

2.3.1 Screening activities performed prior to obtaining informed consent

Minimal risk activities that may be performed before the subject has signed a consent include the following:

- Email, written, in person or telephone communications with prospective subjects
- Review of existing medical records to include H&P, laboratory studies, etc.
- Review of existing MRI, x-ray, or CT images
- Review of existing photographs or videos
- Review of existing pathology specimens/reports from a specimen obtained for diagnostic purposes

2.3.2 Screening activities performed after a consent for screening has been signed

The following activities will be performed only after the subject has signed the study consent OR the consent for study 01-C-0129 (for NIH only provided the procedure is permitted on that study) on which screening activities may also be performed. Assessments performed at outside facilities or on another NIH protocol within the timeframes below may also be used to determine eligibility once a participant has signed the consent.

Within 30 days prior to administration of ¹⁸F-DCFPyL, unless otherwise specified:

- CT and/or MRI (outside imaging studies can be used; however, the images must be made available in DICOM format for review by MIB staff) (within 2 months prior to administration of ¹⁸F-DCFPyL).
- Medical history, concomitant medication review and physical examination (including height, weight, vital signs, and ECOG performance status).
- Hematological profile: CBC with differential and platelet count
- Acute care profile: sodium, potassium, chloride, total CO₂, creatinine, glucose, urea nitrogen, eGFR
- Serum or urine pregnancy test for female participants of childbearing age (in the absence of prior hysterectomy).

2.4 SCREEN FAILURES

Screen failures are defined as participants who consent to participate in the clinical trial but are not subsequently assigned to the study intervention or entered in the study. A minimal set of screen failure information is required to ensure transparent reporting of screen failure participants, to meet the Consolidated Standards of Reporting Trials (CONSORT) publishing requirements and to respond to queries from regulatory authorities. Minimal information includes demography, screen failure details, eligibility criteria, and any serious adverse event (SAE).

Individuals who do not meet the criteria for participation in this trial (screen failure) because prior biopsy did not confirm HCC may be rescreened.

2.5 INTERVENTION ASSIGNMENT PROCEDURES

Cohorts

Number	Name	Description
1	HCC	Participant with radiographically confirmed hepatocellular cancer.

Arms

Number	Name	Description
1	Baseline and Post-treatment Imaging	¹⁸ F-DCFPyL PET/CT imaging, CT and/or MRI and standard of care local treatment.

Arm assignment

Participants in cohort 1 will directly be assigned to arm 1.

3 STUDY IMPLEMENTATION

3.1 STUDY DESIGN

This is an open-label multi-center study recruiting participants with suspected hepatocellular carcinoma (with at least one detectable liver lesion on standard of care CT and/or MRI) who are eligible to undergo local treatment for HCC (e.g., surgical resection, radiofrequency ablation, microwave ablation, transarterial embolization (TAE), stereotactic body radiotherapy (SBRT)). Participants will be consented and enrolled through the NIH Clinical Center.

All participants will undergo a baseline ¹⁸F-DCFPyL PET/CT. Within approximately 2 weeks of each ¹⁸F-DCFPyL PET/CT scan, participants will also be scanned with a ¹⁸F-FDG PET/CT imaging. ¹⁸F-FDG PET/CT may be performed within two weeks before or after each ¹⁸F-DCFPyL PET/CT scan. Each PET/CT imaging must be approximately a day apart. The order obtained for ¹⁸F-DCFPyL PET/CT and ¹⁸F-FDG PET/CT does not matter.

A CT and/or MRI will be performed within 2 months of the ¹⁸F-DCFPyL PET/CT scan. Clinical scans performed in this time frame by local providers are also acceptable.

Participants will undergo a biopsy prior to/concurrent with local therapy (more than one lesion may be biopsied during the same procedure). The procedure may be performed at the NIH Clinical Center or at the participating site (Washington DC Veteran's Affairs Medical Center). The treatment procedure will be scheduled as clinically indicated and samples will be collected prior to therapy (or during surgical resection).

An additional ¹⁸F-DCFPyL PET/CT imaging will be performed during the first routine post local therapy follow-up for participants with a positive baseline ¹⁸F-DCFPyL-PET/CT (i.e. the presence of DCFPyL-avid tumor/s) and with a biopsy confirming HCC diagnosis. Subjects with negative tumor uptake at the baseline ¹⁸F-DCFPyL-PET/CT and with a biopsy confirming HCC, will not have study-related imaging post-treatment and will remain in follow-up. Subjects with biopsies negative for HCC will be taken off protocol.

Participants with a positive HCC biopsy will be followed by clinical chart review, phone-call, email follow-up or any other NIH approved remote platform for tumor markers and radiologic evidence of recurrence over a 5-year period from the last ¹⁸F-DCFPyL PET/CT imaging. A set of imaging (¹⁸F-DCFPyL PET/CT, ¹⁸F-FDG PET/CT, CT/MRI) may be performed and research samples may be collected at the time of tumor recurrence per PI discretion. Should participants undergo another treatment during the follow up period, a biopsy may be done per PI discretion (more than one lesion may be biopsied during the same procedure).

For detailed study and schedule of procedures, refer to section [3.3](#).

3.2 AGENT ADMINISTRATION

3.2.1 ¹⁸F-DCFPyL administration

The target administered activity will be 9 mCi; dose variations will be in accordance with the Nuclear Regulatory Commission (NRC) standard dose variation (i.e. 20%) permitted for diagnostic clinical studies. Due to potential unpredictable delays and the short half-life of ¹⁸F, the total dose of ¹⁸F-DCFPyL administered may be reduced at the discretion of the principal investigator or their designee.

The administration site should be evaluated just before, during and after injection, to assess for extravasation and/or for the presence of signs of local irritation.

Because there is an unknown but potential risk for adverse events in nursing infants secondary to exposure of the mother to ¹⁸F, breastfeeding should be discontinued for 12 hours after administration of either ¹⁸F-DCFPyL or ¹⁸F-FDG.

3.2.2 ¹⁸F-DCFPyL PET/CT imaging

The ¹⁸F-DCFPyL PET/CT imaging will consist of the ¹⁸F-DCFPyL injection, followed by a ~45 min dynamic CT imaging of a single bed position (including the liver lesion), and a static whole-body PET/CT imaging (top of head to mid-thighs) performed at 1 hour (+/- 10 minutes) post ¹⁸F-DCFPyL injection. Only a single injection of ¹⁸F-DCFPyL is required. The initial 45 minutes dynamic regional scan will be used to determine the kinetics of ¹⁸F-DCFPyL within the tumor as compared with normal liver and other background.

Participants will be encouraged to hydrate and urinate frequently after administration of the drug.

Summary of scanning procedure:

1. IV placement
2. Administration of ¹⁸F-DCFPyL; begin AE monitoring
3. Dynamic PET/CT imaging of a single field-of-view (including the liver lesion) will be performed (~ 45 minutes)
4. Subject asked to void
5. 1 hour (+/- 10 minutes) following ¹⁸F-DCFPyL injection, a static whole body PET/CT imaging will be performed (~30-45 minutes in duration)
6. Follow-up AE query ~1-3 days post-injection

3.2.3 ¹⁸F-FDG PET/CT imaging

The ¹⁸F-FDG PET/CT imaging will consist of an ¹⁸F-FDG injection and PET/CT imaging performed approximately 1 hour post ¹⁸F-FDG injection. A corresponding low dose CT scan for attenuation correction and co-registration purposes will be performed prior to the PET image.

3.3 STUDY CALENDAR

Procedures	Screening ¹	Baseline ¹ Study Visit 1	Study Visit 2 ¹⁰	Follow-up ¹¹	Disease Progression
Informed consent	X				
Medical Assessment					
Demographics	X				
Medical history	X				
Concomitant medication review	X				
Physical Assessment					
ECOG	X				
Physical exam (including height and weight)	X				
Vital signs	X	X 2	X 2		
Laboratory Assessment					
Hematology (CBC with diff and platelet)	X		X		
Serum chemistry/Acute Care Panel 3	X		X		
Serum or urine pregnancy test 4	X		X		X
Study Intervention					
CT and/or MRI	X 5		X 5		X 12
¹⁸ F-DCFPyL PET/CT imaging 6		X	X		X 12
¹⁸ F-FDG PET/CT imaging 7		X	X		X 12
Adverse Event Monitoring					
Injection site monitoring 8		X	X		X
Adverse event monitoring/Query 8		X	X		X

Procedures	Screening ¹	Baseline ¹ Study Visit 1	Study Visit 2 ¹⁰	Follow-up ¹¹	Disease Progression
Correlative studies					
Tumor marker tests 9, 13		X	X		X
Exome germline control blood collection		X			
Tumor Biopsy		Concurrent with standard of care therapy (pre-treatment or during surgical resection)			
Blood and urine for EVP analysis 13		X	X	X	X
Follow-up evaluations					
Review of clinical chart, phone call or e-mail (or any NIH approved platform)				X	
Collection/review of imaging scans				X	

1. Performed within 30 days prior to administration of ¹⁸F-DCFPyL unless otherwise indicated. Screening procedures such as medical assessment may be performed remotely via any NIH approved platforms.
2. Vital signs will be taken prior to injection of ¹⁸F-DCFPyL.
3. Acute care panel: sodium, potassium, chloride, total CO₂, creatinine, glucose, urea nitrogen, eGFR
4. For female participants of childbearing age (in the absence of prior hysterectomy). Pregnancy tests may be performed as clinically indicated prior to each scan.
5. CT (Chest/Abdomen/Pelvis) and/or MRI (Abdomen) will be performed within 2 months of each ¹⁸F-DCFPyL PET/CT. Imaging may be performed at certified outside facility and provided to study team.
6. Subjects will undergo ¹⁸F-DCFPyL injection and a dynamic PET/CT. Approximately 1 hour (+/- 10 minutes) post ¹⁸F-DCFPyL injection, a static PET/CT imaging performed. Refer to section **3.2.2** for additional information regarding the scanning procedure.
7. ¹⁸F-FDG PET/CT will be performed within approximately 2 weeks before or after each ¹⁸F-DCFPyL scan. Each PET/CT imaging must be approximately a day apart. The order obtained for ¹⁸F-DCFPyL PET/CT and ¹⁸F-FDG PET/CT does not matter.
8. Event monitoring will be done at the time of injection, and 1 hour post injection. All subjects will be contacted by phone at ~1-3 business days post-injection and will be asked non-leading questions regarding symptoms. At the investigator's discretion, subjects

with safety concerns noted during the post injection period may remain at the site or be asked to return to the site to undergo further safety assessments at the 1-3 business day follow-up time point.

9. Tumor markers include Alpha-fetoprotein, carcinoembryonic antigen, carbohydrate antigen 19.9 (CA19.9) and liver function tests (Alkaline Phosphatase, ALT, AST, Total Bilirubin, Direct Bilirubin). Refer to section **5.1** for more details.
10. Only participants with a positive baseline ¹⁸F-DCFPyL-PET/CT scan (i.e. with the presence of DCFPyL-avid tumor/s) and a biopsy confirming HCC diagnosis will undergo visit 2 for a second ¹⁸F-DCFPyL PET/CT (during routine treatment follow up, typically within 16 weeks).
11. Follow-up will be performed every 3 months (\pm 2 weeks) after the last ¹⁸F-DCFPyL scan (or after therapy for participants with negative baseline ¹⁸F-DCFPyL PET/CT and biopsy confirming HCC) for 2 years, and yearly afterwards for an additional 3 years.
12. If tumor recurrence occurs during the follow-up period, an ¹⁸F-DCFPyL PET/CT, ¹⁸F-FDG PET/CT, CT/MRI and biopsy may be performed any time after recurrence at PI discretion. Biopsy would be performed concurrently with treatment if the latter is performed.
13. Blood collection for tumor markers and EVP analysis may be omitted beyond visit 2 if any issues with scheduling or logistics. The same applies to urine collection for EVP analysis.

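### The only pregnancy test required before the baseline tracers is the screening test, which may be 30 days old at DCFPyL and about 44 days old at FDG; repeat tests are discretionary

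*Combined protocol and SAP*

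**What the plan says.** All references are to the Combined protocol and SAP.

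- **Exclusion.** Section 2.1.2.7 excludes pregnant women because DCFPyL may harm or end a pregnancy.
- **Screening test.** Section 2.3.2 lists a serum or urine pregnancy test among the procedures with the default 30-day window and gives it no tighter limit. Calendar footnote 1 repeats that window: "Performed within 30 days prior to administration of" DCFPyL. Section 2.3.2 also allows results from elsewhere: "Assessments performed at outside facilities or on another NIH protocol within the timeframes below may also be used to determine eligibility".
- **Calendar row.** In section 3.3 the row "Serum or urine pregnancy test 4" is marked at Screening, Study Visit 2 and Disease Progression. The Baseline/Study Visit 1 cell, where both tracers are first given, is blank.
- **Repeat tests.** Footnote 4 adds: "Pregnancy tests may be performed as clinically indicated prior to each scan".
- **FDG timing.** Footnote 7 says that FDG "PET/CT will be performed within approximately 2 weeks before or after each" DCFPyL scan, in either order.
- **A contrasting rule.** Footnote 2 fixes the order for another procedure: "Vital signs will be taken prior to injection of" DCFPyL.
- **Other safeguards.** Section 2.1.1.9 requires contraception "prior to study entry and for 2 months after each study PET/CT imaging" and tells a woman who is, or thinks she may be, pregnant to inform her physician at once. Sections 3.6.2 and 8.5.1 take a pregnant participant off study and stop the intervention.

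**The concern.** The exclusion is firmly worded, but at baseline nothing checks it close to the injections it is meant to guard. Footnote 4 leaves a repeat test to clinical indication, and an early, unsuspected pregnancy gives none. A site that follows every rule could therefore give both baseline tracers to a woman who conceived after her screening test, or whose pregnancy was too early to show on it.

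What is at stake is an avoidable exposure of an embryo to two radiotracers and the accompanying CT. The estimate of positive predictive value, its confidence interval and the sample size do not depend on this.

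**Working it through.** The plan states no figure for test age, so there is none to reproduce. The check is calendar arithmetic on the stated windows.

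**Inputs**

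- Screening window: up to 30 days before DCFPyL (2.3.2; calendar footnote 1).
- FDG window: about 14 days before or after DCFPyL (3.1; calendar footnote 7).
- Marked tests: Screening, Visit 2, Disease Progression (3.3).

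**Baseline: greatest age of the required test**

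- At DCFPyL: 30 days.
- At FDG, if it follows by two weeks: 30 + 14 = about 44 days.
- At FDG, if it comes two weeks first: 30 - 14 = about 16 days. This assumes that the screening test precedes both tracers; the 30-day window is anchored to DCFPyL only.

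The 44 days is a worst case. It needs the oldest permitted test and the latest permitted FDG scan, and it is approximate because the FDG window is.

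**Visit 2 and Disease Progression**

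Footnote 1 is attached to the Screening and Baseline columns only, so the later tests have no stated window and no maximum age can be computed. If the marked test is assumed to be done on the DCFPyL day, FDG may lie anywhere from 14 days before to 14 days after it. The test would then be up to about 14 days old at a later FDG injection, or come up to about 14 days after an earlier one.

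**Do other rules close the gap?**

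| Rule | What it does | Requires a test near injection? |
|---|---|---|
| 2.1.1.9, contraception | Lowers the chance of pregnancy | No |
| 2.1.1.9, report suspicion | Can prompt a test under footnote 4 | Only if pregnancy is suspected |
| 3.6.2 and 8.5.1 | Act once pregnancy is known | No |
| Footnote 4 | Permits a test before a scan | No |

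None of them makes a test mandatory before the baseline injections.

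**The case against.** The best defence is that the plan layers its safeguards in proportion to risk: a screening test, required contraception, a duty to report suspicion, discretionary repeats, and scheduled tests at both later scan visits. For a compliant woman to be injected while pregnant, contraception must fail or go unused, she must suspect nothing, and no discretionary test must be done. The documents set no standard for test age that this breaches, and sites may well test on the day anyway.

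Much of that stands. It makes the event unlikely and keeps the point a modest one. It does not answer the baseline gap, because the remaining case is the unsuspected pregnancy, which only a required test would find.

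Three stronger readings are tempting and should not be drawn:

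- *The later tests have no stated order at all.* Footnote 4 does speak of testing before each scan, and a test marked at a scan visit is naturally read that way. What is missing is a binding order or window.
- *Women's contraception lapses by a known number of days before Visit 2.* The two-month rule in 2.1.1.9 could end before a Visit 2 that is typically within 16 weeks. But the start of those 16 weeks is not stated, so any day count rests on an assumed anchor, and a test is already marked at Visit 2.
- *Fetal harm can be estimated from the dosimetry table.* Section 1.2.1 gives absorbed dose by organ, but the documents offer no basis for turning it into a harm estimate.

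**Conclusion.** The concern holds in this form: at baseline the only required test may be up to 30 days old at DCFPyL and up to about 44 days old at an FDG injection two weeks later, and repeats are optional. At Visit 2 and progression a test is scheduled, but neither its order nor its window is binding, and nothing ties it to FDG.

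The baseline ages rest only on the stated windows, with two weeks taken as 14 days. The number of women of childbearing age is not given, so no expected count of exposed pregnancies is claimed. A reader might infer that the plan tolerates dosing in a known pregnancy; it does not, since 2.1.2.7, 3.6.2 and 8.5.1 all forbid or stop it. The gap is one of verification.

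This is a cheap improvement in patient safety, held with high confidence. It is not a threat to the trial's validity.

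**What to change.** In section 3.3:

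1. Mark the pregnancy test in the Baseline/Study Visit 1 column.
2. Replace the second sentence of footnote 4 with:

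> *A negative urine or serum pregnancy test is required within 24 hours before each 18F-DCFPyL and each 18F-FDG injection; the dose is not given until the result is recorded.*

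The 24 hours is a proposal; another fixed short window would serve.

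**Cost.** Keep the screening test and add one test per injection, two injections per scan set. The extra tests per woman of childbearing age, over those already marked, are:

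- baseline scans only: (1 + 2) - 1 = 2
- with Visit 2: (1 + 4) - 2 = 3
- with recurrence scans as well: (1 + 6) - 3 = 4

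The count is one lower if the screening test itself falls within the window before the first injection. Urine is already planned at these visits for the extracellular-vesicle work, although collection beyond Visit 2 may be omitted. Nothing changes in the sample size, the analysis or the visit schedule.

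Optionally, 2.1.1.9 could state that women's contraception continues without a break through Visit 2. That is a clarification and the fix does not depend on it.
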